4.2. End of Trial Definition

End of the trial is the date of the last visit, last scheduled procedure shown in the Schedule of Activities (Appendix 2), or date of discontinued participation for the last patient.

4.3. Scientific Rationale for Study Design

The scientific rationale for the primary endpoint of this study is based on analyses from 2 large tabalumab SLE Phase 3 trials with a similar patient population involving over 2200 patients (Isenberg et al. 2015; Merrill et al. 2015). The primary endpoint in these trials was SRI-5. The goal of these analyses was to characterize the clinical symptoms most responsible for achieving responder status with SRI-5, and then use this information to design a more efficient trial with clinically relevant endpoints.

To achieve SRI-5, one needs improvement in SLEDAI, with no worsening in BILAG or Physician's Global Assessment of Disease Activity. In the Phase 3 trials, BILAG and Physician's Global Assessment of Disease Activity contributed minimal information to SRI-5, as fewer than 1% of patients achieved a ≥ 5 -point reduction in SLEDAI score, but failed the endpoint due to worsening of BILAG or Physician's Global Assessment of Disease Activity. These data provided the rationale to focus on SLEDAI as the primary driver of clinical response.

The SLEDAI is a weighted disease activity index that measures presence or absence of disease in 9 organ systems. Disease activity in the mucocutaneous, musculoskeletal, or immunologic organ systems was present in over 70% of patients at baseline, with over 98% of patients having mucocutaneous and/or musculoskeletal disease at baseline. In contrast, in the other 6 organ systems these diseases were present in $\leq 15\%$ of patients. These data provided the rationale to focus on mucocutaneous and musculoskeletal disease as the primary driver of clinical response.

The 9 SLEDAI organ systems are composed of specific disease symptoms. The musculoskeletal organ system consists of arthritis and myositis. Arthritis was the most prevalent symptom at baseline ($>80\%$ of patients) while myositis was rare ($\sim 1\%$ of patients). The mucocutaneous organ system includes rash, alopecia, and mucosal ulcer. Rash was the most common symptom in this organ system ($\sim 70\%$ of patients), followed by alopecia ($\sim 55\%$) and mucosal ulcer ($\sim 30\%$). These data, in consultation with SLE experts, provided the rationale to focus on remission of arthritis and rash as the primary endpoint in the clinical trial.

This study is designed to allow for an efficient evaluation of efficacy using clinically relevant endpoints, while still allowing examination of the full range of SLE disease signs and symptoms. SLEDAI, BILAG, and CLASI assessments will be completed at most visits, enabling the evaluation of the entire spectrum of SLE disease activity in this trial, although the primary endpoint is focused on arthritis and rash.

The observation that baricitinib was effective at reducing albuminuria in patients with diabetic kidney disease is also relevant to the design of the trial (Tuttle et al. 2015). As in most SLE trials, patients with severe, active glomerulonephritis are excluded. However, there is interest in collecting preliminary data on a subset of patients to determine if baricitinib has a positive impact on the symptoms of lupus nephritis. Thus, patients with a history of nephritis and current stable renal disease are encouraged to enroll.

This study will be double-blinded and placebo-controlled to minimize bias. The selection of placebo as a comparator for this study is warranted as there are few approved therapies for SLE and all patients in the study are allowed to receive concomitant SoC, including corticosteroids, NSAIDs, antimalarials, and/or immunosuppressants.

In order to minimize the confounding effects of concomitant medications, no increases above baseline are allowed for corticosteroids, immunosuppressants, NSAIDs, or antimalarials during the trial. This strict control over corticosteroids and immunosuppressants is supported by data from the Phase 3 SLE trials discussed above, where less than 20% of patients in any group required an increase in prednisone over the first 24 weeks, and fewer than 10% required an increase in prednisone in the first 8 weeks.

Patients with intolerable or exacerbating disease requiring initiation or increase in doses of corticosteroids, NSAIDs, antimalarials, or immunosuppressants will be discontinued from study treatment and will be treated as nonresponders for the efficacy analyses.

4.4. Justification for Dose

The baricitinib doses of 4-mg and 2-mg administered orally once daily were selected for SLE based on RA studies (JADA [Phase 2] and JADW and JADX [Phase 3]) and a psoriasis study (I4V-MC-JADP, Phase 2) described in the IB.

In these studies, doses of 4-mg and 2-mg daily were generally well tolerated based on the AE profile and infrequent discontinuations of baricitinib dosing. The anticipated on-target, dose-limiting toxicity is a small decline in hemoglobin and hematocrit values resulting from the finding that erythropoietin signals via the JAK2/STAT5 signal transduction pathway (Klingmüller et al. 1997; Vera et al. 2008). This decline in hemoglobin and hematocrit has been seen to occur in higher-dose groups (≥ 8 -mg daily) upon initiation of treatment and then stabilize.

Baricitinib 4-mg and 2-mg daily doses have shown efficacy in RA with an acceptable safety profile. There was no additional efficacy associated with an 8-mg dose in the Phase 2 RA study; thus, only 4-mg and 2-mg have been studied in the RA Phase 3 program. The 4-mg daily dose has demonstrated an earlier onset and a more consistent efficacy than 2-mg daily in RA studies.

In psoriasis, baricitinib doses between 4-mg and 10-mg were associated with statistically significant reductions in measures of disease activity, with greater efficacy at the higher doses. However, the 8-mg and 10-mg doses were associated with a higher rate of AEs related to laboratory abnormalities (decreases in hemoglobin, neutrophils, and lymphocytes), while the 2-mg and 4-mg dose groups had a pattern of AEs similar to placebo. The 2-mg dose did show numeric improvements in efficacy compared with placebo.

The only patient factor thus far that has been identified to have a clinically relevant effect on the PK of baricitinib in completed RA, psoriasis, and DN studies is overall renal function. Although it is currently not clear whether different disease conditions (such SLE versus RA) might result in different PK, aside from varying renal function associated with the disease states, the difference, if any, is not expected to be substantial. It is therefore assumed that exposure at 2-mg and 4-mg in patients with SLE will be similar to that in RA, psoriasis, and DN patients studied, after accounting for renal function. Thus, the highest baricitinib dose to be tested in SLE will be 4-mg, which would be anticipated to show efficacy together with an acceptable safety profile, and also provide the opportunity to cross-reference to the large safety database from the RA Phase 3 program. The lower dose of 2-mg also has the opportunity to show efficacy in SLE.

5. Study Population

Prospective approval of protocol deviations to recruitment and enrollment criteria, also known as protocol waivers or exemptions, are not permitted.

Patients are entered into the study once they have signed the ICF. Patients may be assessed for study entry on the basis of readily available information (that is, information that does not require informed consent from the patient).

5.1. Inclusion Criteria

5.1.1. Entry Criteria

Patients are eligible for entry into the study (eligible to sign the ICF) only if they are anticipated to meet all of the following entry criteria at screening (Visit 1):

Type of Patient and Disease Characteristics

- [1] Are at least 18 years of age.
- [2] Have received a clinical diagnosis of SLE at least 24 weeks prior to screening, meeting at least 4 of the 11 Revised Criteria for Classification of Systemic Lupus Erythematosus according to the 1997 Update of the 1982 ACR (Tan et al. 1982; Hochberg et al. 1997) OR meeting at least 4 of the 2012 SLICC classification criteria (Petri et al. 2012), including at least 1 clinical criterion and 1 immunologic criterion.
- [3] Have history of a positive antinuclear antibody (ANA) or a positive anti-dsDNA (if available).
- [4] Have active arthritis and/or rash due to SLE.

Informed Consent

- [5] Are able to read, understand, and give written informed consent.

5.1.2. Enrollment Criteria

Entered patients are eligible for enrollment into the study (eligible for randomization) only if they continue to meet all of the entry criteria above, and meet all of the following enrollment criteria at the time of randomization (Visit 2):

Type of Patient and Disease Characteristics

- [6] Have a positive ANA (HEp-2 ANA titer $\geq 1:80$) and/or a positive anti-dsDNA (≥ 30 IU) as assessed by a central laboratory at screening.

Note: The ANA and/or anti-dsDNA measurement may be repeated once within approximately 2 weeks of the initial value, and the value resulting from repeat testing may be accepted for enrollment eligibility if it meets the eligibility criterion.

- [7] Have a SLEDAI-2K score ≥ 4 based on clinical symptoms (not including lab values) at randomization.
- [8] Have active arthritis and/or active rash as defined by the SLEDAI-2K at randomization.

5.2. Exclusion Criteria

5.2.1. Entry Criteria

Patients are ineligible for entry into the study (ineligible to sign the ICF) if they are anticipated to meet any of the following entry exclusion criteria at screening (Visit 1):

Medical Conditions

- [9] Have active severe lupus nephritis as defined in exclusion criterion [50].
- [10] Have active severe central nervous system (CNS) lupus as defined in exclusion criterion [51].
- [11] Have experienced a clinically significant thrombotic event within 24 weeks of screening or are on anticoagulants and in the opinion of the investigator are not well controlled.
- [12] Have active fibromyalgia that, in the investigator's opinion, would make it difficult to appropriately assess SLE activity for the purposes of this study.
- [13] Have been treated for or had an active occurrence of a systemic inflammatory condition other than SLE such as, but not limited to, RA, juvenile chronic arthritis, spondyloarthropathy, Crohn's disease, ulcerative colitis, or psoriatic arthritis in the 12 weeks prior to screening.
 - a. Patients with secondary Sjogren's syndrome are not excluded.
- [14] Have had any major surgery within 8 weeks prior to screening or will require major surgery during the study that, in the opinion of the investigator in consultation with Lilly or its designee, would pose an unacceptable risk to the patient.
- [15] Have experienced any of the following within 12 weeks of screening: myocardial infarction (MI), unstable ischemic heart disease, stroke, or New York Heart Association Stage IV heart failure.
- [16] Have a history or presence of cardiovascular, respiratory, hepatic, gastrointestinal, endocrine, hematological, neurological, or neuropsychiatric disorders or any other serious and/or unstable illness that, in the opinion of the investigator, could constitute an unacceptable risk when taking investigational product or interfere with the interpretation of data.
- [17] Are largely or wholly incapacitated permitting little or no self-care, such as being bedridden or confined to wheelchair.
- [18] Have an estimated glomerular filtration rate (eGFR) based on the most recent available serum creatinine of $< 50 \text{ mL}/\text{min}/1.73 \text{ m}^2$ (if available).

- [19] Have a history of chronic liver disease with the most recent available aspartate aminotransferase (AST) or alanine aminotransferase (ALT) >2 times the upper limit of normal (>2 x ULN) or the most recent available total bilirubin ≥ 1.5 x ULN (if available).
- [20] Have a history of lymphoproliferative disease; or have signs or symptoms suggestive of possible lymphoproliferative disease, including lymphadenopathy or splenomegaly (other than primarily due to SLE); or have active primary or recurrent malignant disease; or have been in remission from clinically significant malignancy for <5 years.
- Patients with cervical carcinoma in situ that has been resected with no evidence of recurrence or metastatic disease for at least 3 years may participate in the study.
 - Patients with basal cell or squamous epithelial skin cancers that have been completely resected with no evidence of recurrence for at least 3 years may participate in the study.
- [21] Have a current or recent (<4 weeks prior to screening) clinically serious viral, bacterial, fungal, or parasitic infection.
- Note: For example, a recent viral upper respiratory tract infection or uncomplicated urinary tract infection should not be considered clinically serious.
- [22] Have had symptomatic herpes zoster infection within 12 weeks prior to screening.
- [23] Have a history of disseminated/complicated herpes zoster (for example, multidermatomal involvement, ophthalmic zoster, CNS involvement, or post-herpetic neuralgia).
- [24] In the opinion of the investigator, are at an unacceptable risk for participating in the study.
- [25] Have active or chronic viral infection from hepatitis B virus (HBV), hepatitis C virus (HCV), or human immunodeficiency virus (HIV).
- [26] Have had household contact with a person with active tuberculosis (TB) and did not receive appropriate and documented prophylaxis for TB.
- [27] Have evidence of active TB or have previously had evidence of active TB and did not receive appropriate and documented treatment.

Prior/Concomitant Therapy

- [28] Are currently receiving oral corticosteroids at doses >20-mg per day of prednisone (or equivalent) or have adjusted the dose of corticosteroids within 2 weeks of planned randomization.
- [29] Have received topical corticosteroids, other than stable doses of class 6 (mild, such as desonide) or class 7 (least potent, such as hydrocortisone), within 2 weeks of screening or within 4 weeks of planned randomization.

- [30] Have received oral or parenteral [intravenous (IV) or intramuscular (IM)] corticosteroids at doses >40-mg per day of prednisone (or equivalent) within 6 weeks of screening or within 8 weeks of planned randomization, or are anticipated to require parenteral injection of corticosteroids during the study.
- [31] Have had a joint injected with intra-articular corticosteroids or hyaluronic acid within 2 weeks of screening or within 4 weeks of planned randomization.
- [32] Have started treatment with or adjusted the dose of NSAIDs (for which the NSAID use is intended for treatment of signs and symptoms of SLE) within 2 weeks of screening or within 4 weeks of planned randomization.
- [33] Have started treatment with or adjusted the dose of an antimalarial (such as hydroxychloroquine, chloroquine, quinacrine) within 10 weeks of screening or within 12 weeks of planned randomization.
- [34] Have started treatment with or adjusted the dose of an immunosuppressant (such as MTX, azathioprine, mycophenolate) within 10 weeks of screening or within 12 weeks of planned randomization.
- [35] Have received cyclophosphamide (or any other cytotoxic agent) within 12 weeks prior to screening.
- [36] Have received etanercept, infliximab, certolizumab, adalimumab, golimumab, or anakinra within 12 weeks of screening; tocilizumab, abatacept, ustekinumab, rituximab, belimumab, or any other B cell targeted therapies (approved or investigational) within 24 weeks of screening; or any other biologic therapy within 4 weeks or 5 half-lives of screening, whichever is longer.
- [37] Have received intravenous immunoglobulin (IVIg) within 24 weeks of screening.
- [38] Have received plasmapheresis within 12 weeks of screening.
- [39] Have been exposed to a live vaccine within 12 weeks prior to planned randomization or are expected to need/receive a live vaccine during the course of the study (with the exception of herpes zoster vaccination).
 - a. All patients who have not received the herpes zoster vaccine at screening will be encouraged (per local guidelines) to do so prior to randomization; vaccination must occur >4 weeks prior to randomization and start of investigational product. Patients will be excluded if they were exposed to herpes zoster vaccination within 4 weeks of planned randomization.
 - b. Investigators should review the vaccination status of their patients and follow the local guidelines for vaccination of those ≥ 18 years of age with nonlive vaccines intended to prevent infectious disease prior to entering patients into the study.

Other Exclusions

- [40] Are pregnant or nursing at the time of screening.

- [41] Are females of childbearing potential who do not agree to use 2 forms of highly effective birth control when engaging in sexual intercourse with a male partner while enrolled in the study and for at least 4 weeks following the last dose of investigational product.
- a. Females of nonchildbearing potential are defined as women ≥ 60 years of age, women ≥ 40 and < 60 years of age who have had a cessation of menses for at least 12 months, or women who are congenitally or surgically sterile (that is, have had a hysterectomy or bilateral oophorectomy or tubal ligation).
 - b. The following birth control methods are considered highly effective (the patient should choose 2 to be used with their male partner):
 - oral, injectable, or implanted hormonal contraceptives
 - condom with a spermicidal foam, gel, film, cream, or suppository
 - occlusive cap (diaphragm or cervical/vault caps) with a spermicidal foam, gel, film, cream, or suppository
 - intrauterine device
 - intrauterine system (for example, progestin-releasing coil)
 - vasectomized male (with appropriate post-vasectomy documentation of the absence of sperm in the ejaculate)

Note: When local guidelines concerning highly effective methods of birth control differ from the above, the local guidelines must be followed.
- [42] Are males who do not agree to use 2 forms of highly effective birth control (see above) while engaging in sexual intercourse with female partners of childbearing potential while enrolled in the study and for at least 4 weeks following the last dose of investigational product.
- [43] Have donated more than a single unit of blood within 4 weeks prior to screening or intend to donate blood during the course of the study.
- [44] Have a history of chronic alcohol abuse, IV drug abuse, or other illicit drug abuse within the 2 years prior to screening.
- [45] Have previously been randomized in this study or any other study investigating baricitinib.
- [46] Are unable or unwilling to make themselves available for the duration of the study and/or are unwilling to follow study restrictions/procedures.
- [47] Are currently enrolled in, or discontinued within 4 weeks prior to screening from any other clinical trial involving an investigational product or nonapproved use of a drug or device or concurrently enrolled in any other type of medical research judged not to be scientifically or medically compatible with this study.

- [48] Are investigator site personnel directly affiliated with this study and/or their immediate families. Immediate family is defined as a spouse, parent, child, or sibling, whether biological or legally adopted.
- [49] Are Lilly or Incyte employees or either's designee.

5.2.2. Enrollment Criteria

Entered patients are ineligible for enrollment into the study (ineligible for randomization) and should be discontinued from the study if they meet any of the entry exclusion criteria above, or meet any of the following enrollment exclusion criteria at the time of randomization (Visit 2):

Medical Conditions

- [50] Have severe active lupus nephritis, including urine protein/creatinine ratio >300 mg/mmol (as an estimate of approximate proteinuria >3g/day) or active urinary sediment with red blood cell cast(s), or histological evidence (if available) of diffuse proliferative glomerulonephritis within the 12 weeks prior to screening.

Note: The lab measurements related to lupus nephritis may be repeated once within approximately 2 weeks of the initial values, and the values resulting from repeat testing may be accepted for enrollment eligibility if they meet the eligibility criterion.

- [51] Have active severe CNS lupus including aseptic meningitis, cerebral vasculitis, demyelinating syndrome, myelopathy, acute confusional state, psychosis, acute inflammatory demyelinating polyradiculoneuropathy, mononeuropathy (single/multiplex), cranial neuropathy, plexopathy, status epilepticus, or cerebellar ataxia.
- [52] Have symptomatic herpes simplex at the time of randomization.
- [53] Have screening electrocardiogram (ECG) abnormalities that, in the opinion of the investigator or the sponsor, are clinically significant and indicate an unacceptable risk for the patient's participation in the study.
- [54] Have evidence of active TB as documented by a positive purified protein derivative (PPD) test (≥ 5 -mm induration between approximately 2 and 3 days after application, regardless of vaccination history), medical history, clinical symptoms, and abnormal chest x-ray at screening.
- The QuantiFERON®-TB Gold test or T-SPOT®.TB test (as available and if compliant with local TB guidelines) may be used instead of the PPD test. Patients are excluded from the study if the test is not negative and there is clinical evidence of active TB.
- [55] Have evidence of latent TB (as documented by a positive PPD test, no clinical symptoms consistent with active TB, and a normal chest x-ray at screening, or as outlined below) unless patient completes at least 4 weeks of appropriate treatment prior to randomization and agrees to complete the remainder of treatment while in the trial.

- If the PPD test is positive and the patient has no medical history or chest x-ray findings consistent with active TB, the patient may have a QuantiFERON®-TB Gold test or T-SPOT®.TB test (as available and if compliant with local TB guidelines). If the test results are not negative, the patient will be considered to have latent TB (for purposes of this study) and will be excluded.
- The QuantiFERON®-TB Gold test or T- SPOT®.TB test (as available and if compliant with local TB guidelines) may be used instead of the PPD test. If the test results are positive, the patient will be considered to have latent TB and will be excluded. If the test is not negative, the test may be repeated once within 2 weeks of the initial value. If the repeat test results are again not negative, the patient will be considered to have latent TB (for purposes of this study) and will be excluded.
- Exceptions include patients with a history of active or latent TB who have documented evidence of appropriate treatment and with no history of re-exposure since their treatment was completed. (Such patients would not be required to undergo the protocol specific TB testing for PPD, QuantiFERON®-TB Gold test or T-SPOT®.TB test, but would still require a baseline chest x-ray.)

[56] Have a positive test for HBV defined as:

- a. positive for hepatitis B surface antigen (HBsAg), or
- b. positive for anti-hepatitis B core antibody (HBcAb) but negative for hepatitis B surface antibody (HBsAb), or
- c. positive for HBcAb and positive for hepatitis B virus deoxyribonucleic acid (HBV DNA)
- d. Patients in Japan (or elsewhere if required), are excluded if they are positive for HBsAg; or, are positive for HBcAb and/or HBsAb and positive for HBV DNA.

If any of the HB tests have an indeterminate result, confirmatory testing will be performed by an alternate method.

[57] Have HCV (positive for anti-hepatitis C antibody with confirmed presence of HCV).

[58] Have evidence of HIV infection and/or positive HIV antibodies.

Diagnostics Assessments

[59] Have screening laboratory test values, including thyroid-stimulating hormone (TSH), outside the reference range for the population or investigative site that, in the opinion of the investigator, pose an unacceptable risk for the patient's participation in the study.

- Patients who are receiving thyroxine as replacement therapy may participate in the study, provided stable therapy has been administered for ≥ 12 weeks and TSH is within the laboratory's reference range. Patients who are receiving stable thyroxine replacement therapy who have TSH marginally outside the laboratory's normal reference range may participate if the treating physician has documented that the thyroxine replacement therapy is adequate for the patient.

Laboratory tests may be repeated once within approximately 2 weeks of the initial value, and the value resulting from repeat testing may be accepted for enrollment eligibility if it meets the eligibility criterion.

[60] Have any of the following specific abnormalities on screening laboratory tests:

- a. ALT or AST >2 x ULN
- b. total bilirubin ≥ 1.5 x ULN
- c. hemoglobin <9 g/dL (90.0 g/L)
- d. total white blood cell (WBC) count <2500 cells/ μ L ($<2.50 \times 10^3/\mu$ L or <2.50 GI/L)
- e. neutropenia (absolute neutrophil count [ANC] <1200 cells/ μ L) ($<1.20 \times 10^3/\mu$ L or <1.20 GI/L)
- f. lymphopenia (lymphocyte count <750 cells/ μ L) ($<0.75 \times 10^3/\mu$ L or <0.75 GI/L)

Note: Patients may be enrolled with a lymphocyte count <750 cells/ μ L but ≥ 500 cells/ μ L ($<0.50 \times 10^3/\mu$ L or <0.50 GI/L) if the low lymphocyte count is considered by the investigator to be a result of the underlying SLE disease or concomitant medications.

- g. thrombocytopenia (platelets $<50,000$ cells/ μ L) ($<50 \times 10^3/\mu$ L or <50 GI/L)
- h. eGFR (Modification of Diet in Renal Disease [MDRD]) <50 mL/min/1.73 m².

In the case of any of the aforementioned laboratory abnormalities, the tests may be repeated once within approximately 2 weeks of the initial values, and values resulting from repeat testing may be accepted for enrollment eligibility if they meet the eligibility criterion.

Other Exclusions

- [61] Are women ≥ 40 and <60 years of age who have had a cessation of menses for at least 1 year, have a follicle-stimulating hormone (FSH) value <40 mIU/mL, and do not agree to use 2 forms of highly effective methods of birth control when engaging in sexual intercourse with a male partner while enrolled in the study and for at least 4 weeks following the last dose of investigational product, unless they are congenitally or surgically sterile (that is, have had a hysterectomy, bilateral oophorectomy, or tubal ligation).

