7.1. Discontinuation from Study Treatment

7.1.1. Interruption of Investigational Product

In some circumstances, it may be necessary to temporarily interrupt treatment as a result of AEs or abnormal laboratory values that may have an unclear relationship to investigational product. Except in cases of emergency, it is recommended that the investigator consult with Lilly (or its designee) before temporarily interrupting therapy for reasons other than those defined in [Table JAHH.3](#) below. Retest timing and frequency is at the investigator's discretion.

The investigator must obtain approval from Lilly (or its designee) before restarting investigational product that was temporarily discontinued because of an AE or abnormal laboratory value. Investigational product must be held in the following situations and may be resumed as noted in [Table JAHH.3](#).

Table JAHH.3. Criteria for Temporary Interruption of Investigational Product

Hold investigational product if the following laboratory test results occur:	Investigational product may be resumed after approval from Lilly (or its designee) when:
WBC count <2000 cells/ μ L (<2.00x10 ³ / μ L or <2.00 GI/L)	WBC count \geq 2500 cells/ μ L (\geq 2.50x10 ³ / μ L or \geq 2.50 GI/L)
ANC <1000 cells/ μ L (<1.00x10 ³ / μ L or <1.00 GI/L)	ANC \geq 1200 cells/ μ L (\geq 1.20x10 ³ / μ L or \geq 1.20 GI/L)
Lymphocyte count <500 cells/ μ L (<0.50x10 ³ / μ L or <0.50 GI/L) Note: IP can be continued with a lymphocyte count <500 cells/ μ L but \geq 300 cells/ μ L (<0.30x10 ³ / μ L or <0.30 GI/L) if the low lymphocyte count is considered by the investigator to be a result of the underlying SLE disease or concomitant medications. IP must be held for lymphocyte count <300 cells/ μ L, regardless of cause.	Lymphocyte count \geq 750 cells/ μ L (\geq 0.75x10 ³ / μ L or \geq 0.75 GI/L) Note: If IP is held for lymphocyte count <300 cells/ μ L, it may be resumed after approval from Lilly (or its designee) when the lymphocyte count is \geq 500 cells/ μ L if the low lymphocyte count is considered by the investigator to be a result of the underlying SLE disease or concomitant medications.
Platelet count <25,000/ μ L (<25x10 ³ / μ L or <25 GI/L)	Platelet count \geq 50,000/ μ L (\geq 50x10 ³ / μ L or \geq 50 GI/L)
eGFR <40 mL/min/1.73 m ² (from serum creatinine)	eGFR \geq 50 mL/min/1.73 m ²
ALT or AST >5 x ULN	ALT and AST return to <2 x ULN, and IP is not considered to be the cause of enzyme elevation

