Hemoglobin <8 g/dL (<80.0 g/L)	Hemoglobin \geq 9 g/dL (\geq 90.0 g/L)
Symptomatic herpes zoster	All skin lesions have crusted and are resolving
Severe infection that, in the opinion of the investigator, merits the IP being discontinued	Resolution of infection

Abbreviations: ALT = alanine aminotransferase; ANC = absolute neutrophil count; AST = aspartate aminotransferase; eGFR = estimated glomerular filtration rate; IP = investigational product; ULN = upper limit of normal; WBC = white blood cell.

7.1.2. *Permanent Discontinuation of Investigation Product*

Any patient who is permanently discontinued from investigational product for an AE or abnormal laboratory result should have the reason for investigational product discontinuation reported as the AE or abnormal laboratory value.

Discontinuation of the investigational product for abnormal liver tests **should be considered** by the investigator when a patient meets one of the following conditions after consultation with the Lilly designated medical monitor:

- ALT or AST >8 x ULN
- ALT or AST >5 x ULN for more than 2 weeks after temporary interruption of investigational product
- ALT or AST >3 x ULN and either total bilirubin level (TBL) >2 x ULN or INR >1.5 x ULN
- ALT or AST >3 x ULN with the appearance of fatigue, nausea, vomiting, right upper-quadrant pain or tenderness, fever, rash, and/or eosinophilia (>5%)
- alkaline phosphatase (ALP) >3 x ULN
- ALP >2.5 x ULN and TBL >2 x ULN
- ALP >2.5 x ULN with the appearance of fatigue, nausea, vomiting, right upper quadrant pain or tenderness, fever, rash, and/or eosinophilia (>5%).

Patients should be discontinued from the investigational product in the following circumstances:

- WBC count <1000 cells/ μ L ($1.00 \times 10^3 / \mu$ L or 1.00 GI/L)
- ANC <500 cells/ μ L ($0.50 \times 10^3 / \mu$ L or 0.50 GI/L)
- Lymphocyte count <200 cells/ μ L ($0.20 \times 10^3 / \mu$ L or 0.20 GI/L)
- Hemoglobin <6.5 g/dL (<65.0 g/L).

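### Two lymphocyte limits, one for enrolment and one for continuing drug, carry opposite inequality signs in their cells/µL and GI/L forms

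*Protocol*

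**What the plan says.** **Enrolment (Section 5.2.2, [60]f Note).** The exclusion itself is a count under 750 cells/µL. The Note makes an exception: "Patients may be enrolled with a lymphocyte count <750 cells"/µL, provided the count is at least 500 cells/µL and the investigator attributes it to SLE or to concomitant medication. The lower limit is then glossed in brackets as <0.50 × 10³/µL, "or <0.50 GI/L) if the low lymphocyte count is considered by the investigator to be a result of the underlying SLE disease".

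**Interruption (Section 7.1.1, Table JAHH.3).** The hold trigger is a count under 500 cells/µL, and its bracket runs straight into the Note: "or <0.50 GI/L) Note: IP can be continued with a lymphocyte count <500 cells"/µL. The Note requires at least 300 cells/µL for that exception and glosses this limit as <0.30 × 10³/µL, "or <0.30 GI/L) if the low lymphocyte count is considered by the investigator". The sentence after it reads "IP must be held for lymphocyte count <300" cells/µL, whatever the cause. The resume cell in the same row has its own Note, beginning "Note: If IP is held for lymphocyte count <300 cells"/µL; it uses ≥500 cells/µL as the resume level, with no bracket.

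**Discontinuation (Section 7.1.2).** The lymphocyte limit is "Lymphocyte count <200 cells"/µL, with 0.20 GI/L in brackets and no sign.

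**The concern.** The brackets should be conversions of the cells/µL figures. In these two Notes they state the reverse condition. A reader working in GI/L meets a rule that admits, or keeps on drug, the patients below the limit that the cells/µL form sets.

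These limits are meant to be applied as written. Section 5 allows no prospective waivers of enrolment criteria, so the printed text is what sites apply and what deviations are judged against. Lymphopenia is also among the events of special interest in Section 8.2.2.

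The same bracket also has two meanings. In Table JAHH.3, <0.50 GI/L is the equivalent of the hold trigger. In the [60]f Note it stands for permission to enrol.

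**Working it through.** No figure in the sample-size section bears on this. The check is a unit conversion followed by a comparison of ranges.

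**Step 1: conversion.** 1 GI/L = 10³/µL = 1000 cells/µL. So 500 cells/µL = 500/1000 = 0.50 GI/L, 300 cells/µL = 0.30 GI/L and 200 cells/µL = 0.20 GI/L. All magnitudes agree, so the discrepancy lies in the signs alone.

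**Step 2: ranges, read literally, in whole counts (cells/µL).**

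| Exception | cells/µL form | Bracket form | Values in both |
|---|---|---|---|
| Enrolment, [60]f Note | ≥500 and <750: 500–749 | <0.50 GI/L: 0–499 | none |
| Continue drug, Table JAHH.3 Note | ≥300 and <500: 300–499 | <0.30 GI/L: 0–299 | none |

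With the same sign in both unit forms, each pair would define the same range.

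**Step 3: against the other lymphocyte limits.**
- Enrolment, cells/µL form (500–749): no value meets the Table JAHH.3 hold trigger (<500).
- Enrolment, bracket form (0–499): every value meets that trigger. Of these, 0–299 also fall under the hold that applies whatever the cause, and 0–199 under the Section 7.1.2 discontinuation limit.
- Continue drug, bracket form (0–299): every value falls under the hold in the very next sentence, and 0–199 under the discontinuation limit.

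**Step 4: is this a text-extraction fault?** Unlikely. The reversed sign appears in both bracketed forms (10³/µL and GI/L) of both Notes, while the ≥ sign survives in the main value beside each one and in the resume column of the same table row. Elsewhere in [60]d–g and Table JAHH.3, a bracket that carries a sign carries the same sign as its main value (for example, WBC ≥2500 cells/µL with ≥2.50 GI/L in the resume column). These two Notes are the exceptions.

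**The case against.** The best reply is that this is an editorial slip which the document resolves for itself.

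- With the bracket's sign, the enrolment exception would read as below 750 but below 500, which leaves the 750 with no purpose. The same argument applies to 500 and 300 in Table JAHH.3.
- Table JAHH.3 states the hold below 300 cells/µL outright in the next sentence.
- For the enrolment Note, the resume cell offers support: it uses ≥500 cells/µL as a lower limit under nearly the same attribution to SLE or concomitant medication. The bracket, taken literally, would admit only patients already at the hold trigger.
- The brackets are unit glosses, and some in the protocol carry no sign at all (hemoglobin in [60]c; the WBC, ANC and lymphocyte limits in Section 7.1.2). Two different rules were plainly not intended.
- Other safeguards limit the reach: exclusion [59] on unacceptable screening values, sponsor approval before restarting, and central assay of samples used to decide on resumption.
- Counting values only restates that the sign is reversed.

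Most of this stands, and it bears on weight. Intent can be inferred, nothing shows that a site would follow the bracket and ignore the adjacent figure, and the ranges in Step 2 measure a conflict of text rather than risk to patients. It does not remove the error. The resume cell concerns restarting drug and does not define eligibility, and the [60]f Note has no sentence of its own that settles the matter.

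**Conclusion.** The point holds. Two operative lymphocyte limits are printed with opposite signs in their two unit forms, and no count satisfies both forms of either limit. The enrolment Note needs correction most, because no following sentence states its limit again as one does in Table JAHH.3.

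The fault should be fixed, but its practical reach is small. The protocol does not give the share of patients with counts in these ranges, so no number of affected patients can be stated. Power, the analysis population and the primary analysis are unaffected. The conclusion rests on the printed signs being the sponsor's own, which their repetition in both Notes and both bracketed units supports. It takes no view on which lymphocyte limit is clinically right.

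**What to change.** Reconcile the [60]f Note and the lymphocyte Note in Table JAHH.3 so that the cells/µL, 10³/µL and GI/L forms state the same limit in the same direction. The sponsor's clinical team should confirm each limit. Read both Notes against the hold and resume wording in Table JAHH.3 and the lymphocyte discontinuation limit in Section 7.1.2, so that the whole sequence of limits is consistent. Then notify sites of the correction.

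The cost is a text change in two Notes and a site notice. The design, sample size and analysis stay as they are.
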